- Fatigue: measured using original or modified forms of Cancer Related Fatigue (CRF) scales
- Rating of Perceived Exertion (RPE)
- Quantified measures via portable force plate: medial-lateral sway area, range, mean and variability during bilateral static standing with eyes closed[20]
- Timed-Up-and-Go (TUG)[30,31]
- Quantitative gait stability measures via portable motion capture system: average and variability measures of spatiotemporal gait parameters (e.g., stride length, stride time, step width)[22]*
- Mini-BEST[32]*
- Grip strength[33]*
- Goal Attainment Scale (GAS)[34]*
- Activities of Daily Living (ADL) [35] (e.g., Lawton-Brody iADL, Functional Status Questionnaire (FSQ) ADL, Katz ADL, QuickDASH[36])*
- Functional Fitness of Older Adults test [37]*
- Non-invasive Electroencephalography (EEG)*

Data collected within-session (before and after each session unless otherwise noted):

- Adverse events (before every session)
- Neuropathy: measured using original or modified forms of the EORTC CIPN-20[16]

- Sports Concussion Assessment Test (SCAT) Symptom inventory (for comparison to CIPN-20)[27,28]
- Pain: measured using original or modified forms of the Brief Pain Inventory (BPI)[29]
- Fatigue: measured using original or modified forms of Cancer Related Fatigue (CRF) scales
- Rating of Perceived Exertion (RPE)
- Quantified measures via portable force plate: medial-lateral sway area, range, mean and variability during bilateral static standing with eyes closed[20]
- satisfaction with intervention via 7-pt Likert Scale (after every session)[38]
- Goal Attainment Scale (GAS)[34] (before session, no more than once a week)
- Intrinsic Motivation Inventory (IMI)[39] (after session, no more than once a week)

Data collected by participant at home, daily, and reported to research staff on weekly basis:

We will ask participants to track the adverse event of falls or loss of balance using a daily journal that they take home with them or secure electronic data capture interface (e.g., REDCap, MyCap). We will collect these data weekly during the intervention, and for 6 months following the completion of intervention, through weekly check-ins with all participants

D. Detailed Study Procedures

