b. Secondary measures: Posture (other): will be calculated from the 30s duration of quiet standing data including COP ellipse area, velocity, and sample entropy[38]. In particular, the non-linear measure of sample entropy[38,51–54] may provide additional information regarding complexity of postural control regulation among cancer survivors with neuropathy. **Balance:** is a critical measure of clinical impact. The Timed Up-and-Go test, or **TUG**, (<2 min to administer) is a timed test of a person's ability to stand from a chair, walk 10 feet, turn around, and return to sitting with shorter times indicating better functional

balance. While our data indicate some clinical tests are not sensitive to chemotherapy-induced neuropathy state (e.g., Berg), Wampler et al (2007); Marshall et al. (2017); and Evans et al. (2019) reported that TUG time distinguished cancer survivors with neuropathy (n=20, 8, & 20 survivors respectively) from age-matched controls. **Patient-reported outcomes (PROs):** are critical secondary measures that will help us to understand participant perception of change with intervention. These will be collected 2x/week during multiple baseline testing then monthly thereafter with a subset captured per session to evaluate within-session effects. We will administer PROs during multiple baseline and monthly testing through retention. CIPN-20 and BPI instruments will be administered to complement one another: the CIPN 20 focuses on the effect of neuropathy symptoms on functional capacity while the BPI assesses pain symptoms. We will also collect the symptom inventory from the Sports Concussion Assessment Tool (SCAT). Additionally, we will document cancer-related fatigue (CRF), quality of life (SF-36), satisfaction with intervention, likelihood of recommending the intervention to a friend with neuropathy (this will be included as a question on the satisfaction with intervention survey), perceived benefit, intrinsic motivation, depression/apathy/ anxiety (PRO-CTCAE), and adverse events including falls. **Falls:** each participant will use a diary format to report daily changes in falls, symptoms, use of assistive devices, and amount of concurrent medication use during the study period. These factors will also be recorded by research staff within adverse event reporting 2x per week before Tango lessons. For 6 months after intervention completion, we will collect falls incidence weekly from participant daily dairy records.

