Feedback is used to improve future sessions. Monthly, we prompt participants to rate the likelihood of future engagement. **The Intrinsic Motivation Inventory (IMI)** was developed from the perspective of Self Determination Theory to assess 7 dimensions of experience: Interest/Enjoyment, Perceived Competence, Effort/Importance, Pressure/Tension, and Choice[39,57–61]. We administer the 9 item short form of the IMI weekly to optimize instruction around high Perceived Competence and low Pressure/Tension[58,59] as well as explore relationships between adherence, motor effects, and IMI dimensions (including perceived benefit (Effort/Importance)). The Patient-Reported Outcome version of the **Common Terminology Criteria for Adverse Events v5 (PRO-CTCAE):** developed by NCI, is standard protocol in oncology to screen for signs of depression, anxiety, and apathy associated with cancer treatment or progression[62]. While not an outcome measure, we collect this staff-administered assessment per visit for adverse event screening, using the data to monitor and compare descriptive

statistics between groups. Changes in depression, anxiety, or apathy identified within check-ins, will be addressed.

c. *Within-Session Effects* Posture: will be captured before and after each Tango session in order to assess within-session change over time. A subset of **PROs**: (i.e., CIPN-20, BPI, and CRF) will be collected routinely before and after Tango training to allow analysis of within-session change. Finally, satisfaction with intervention will be collected after each session

Aim2: We will evaluate change in gait variability after 16 sessions of Tango (exp) vs HEX (control) (n=26 per group; 1:1 randomization). As secondary measures, we will analyze local and orbital dynamic stability (pre, post, and 1mo post-intervention), PROs (monthly), and falls incidence (weekly) following intervention completion. **Hypothesis:** At primary endpoint, members of the exp group will improve more relative to control group members in gait variability (i.e., stride-to-stride variability in speed).

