For **Aim 1**, a linear mixed effects model will be used to model postural sway (RMSml). Fixed effects will be included for time, treatment, treatment-by-time interactions, and concurrent medication use. Random effects for subjects will be used to account for correlation between observations from the same subject. The primary estimand will be a difference-in-difference representing the difference in mean RMSml change from baseline to week 16 between treatment groups. While we expect balance between the two groups due to randomization, we will adjust for potential confounders including baseline RMSml, age, body mass index, concurrent medications (e.g., duloxetine) and other variables if imbalance between groups occurs by chance. Similar analyses will be performed for the PROs sensory symptoms (CIPN-20), pain (BPI-SF), fatigue (0–10 Likert), quality of life (SF-36), and falls incidence following intervention completion. Finally, Pearson's R will be calculated to correlate postural control and balance outcomes, PROs, and future falls incidence.

For **Aim 2**, a similar analysis strategy will be used to compare biomechanical mobility between the two groups (linear mixed models; one-sided hypothesis test) as well as the correlation between biomechanical mobility outcomes, PROs, and falls incidence following intervention completion (Pearson's R).

Not all enrolled subjects will complete the intervention and have follow-up data. The linear mixed model analyses can use available data from all participants with at least one observation, regardless of whether or not they complete follow-up. We will compare the baseline characteristics of subjects who complete the study to those who drop out to assess the potential for attrition bias. A sensitivity analysis will be performed using multiple imputation to assess the impact drop-out has on study conclusions.

V. Funding

This project was funded, initially in Phase 1, through a 2015-16 Pelotonia Undergraduate Fellowship. We secured Phase 2 funding in 1R21AG068831 through the NIH National Institute of Aging (Note: this includes visit reimbursement for cancer survivors only).

VI. References

- [1] S.M. Monfort, X. Pan, R. Patrick, J. Singaravelu, C.L. Loprinzi, M.B. [name], A.M.W. Chaudhari, Natural history of postural instability in breast cancer patients treated with taxane-based chemotherapy: A pilot study, *Gait and Posture*. (2016). <https://doi.org/10.1016/j.gaitpost.2016.06.011>.

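### No between-arm comparison of falls during the training period is planned, although both arms keep a daily falls diary throughout it

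*Combined protocol and SAP*

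**What the plan says.** **Collection.** Section IV.C (data collected at home) says participants will "track the adverse event of falls or loss of balance using a daily journal" or use an electronic equivalent. The timing and coverage follow: "We will collect these data weekly during the intervention, and for 6 months following the completion of intervention, through weekly check-ins with all participants". Section IV.D, Aim 1 b, confirms that "each participant will use a diary format to report daily changes in falls" over the study period. It then adds a second route: "These factors will also be recorded by research staff within adverse event reporting 2x per week before Tango lessons". No matching staff schedule is given for the home-exercise (HEX) arm.

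**Outcome.** In section IV.D, the falls measure for Aim 1 is weekly incidence over the 6 months after completion, and the Aim 2 measure is likewise placed after completion.

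**Analysis.** Section IV.F extends the Aim 1 mixed-model approach to several patient-reported outcomes, ending with "quality of life (SF-36), and falls incidence following intervention completion". The remaining uses of falls in IV.F are Pearson correlations with future or post-completion falls, which do not compare arms.

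**Other adverse events.** Section IV.D, Aim 1 b, says of the PRO-CTCAE that it is collected per visit, "using the data to monitor and compare descriptive" statistics between groups. The same text describes it as a screen for depression, anxiety and apathy. Section IV.C lists the PRO-CTCAE and falls as separate adverse-event items.

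**The concern.** Section IV.B requires postural control outside a reference range, so the randomised survivors have impaired balance by design. Falls are a foreseeable harm of any balance training in such a group, and the training period is when the interventions are actually being delivered. Yet the stated falls window begins only when training ends. The randomised comparison of falls would therefore describe what happens after exposure and be silent about exposure itself, even though the diary supplies the data for both arms.

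At stake is the completeness of the safety conclusion. A reader shown only the post-intervention falls result could not tell whether falls during training were similar, fewer or more frequent with Tango.

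**Working it through.** The plan gives no fall rate, falls sample size or falls power, so there is no figure of its own to reproduce. The check has three steps.

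**1. Where falls data are used, by period**

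| Item | During training | After training |
|---|---|---|
| Diary and weekly check-in, all participants (IV.C, IV.D) | yes | yes, 6 months |
| Falls outcome, Aims 1 and 2 (IV.D) | no | yes |
| Between-arm falls analysis (IV.F) | no | yes |
| Correlations with falls (IV.F) | no | yes |
| Descriptive group comparison (IV.D) | PRO-CTCAE; falls not named | same |

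**2. Diary time left out**

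The length of training is unclear. Sixteen sessions at the twice-weekly lesson frequency in IV.D take 16/2 = 8 weeks, but the primary estimand in IV.F is set at week 16. Taking 6 months as 26 weeks:

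- 8 weeks of training: 8/(8 + 26) = 8/34 = 24%.
- 16 weeks of training: 16/(16 + 26) = 16/42 = 38%.

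With 26 per arm, that is 26 × 8/52 = 4.0 or 26 × 16/52 = 8.0 person-years per arm, against 26 × 26/52 = 13.0 afterwards.

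*Illustration only.* Assume a Tango:HEX rate ratio of 0.8 after training, a constant HEX rate, and an in-training ratio R. The whole-period ratio is (w × R + 26 × 0.8)/(w + 26), where w is weeks of training.

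| R (assumed) | w = 8 | w = 16 | Planned analysis shows |
|---|---|---|---|
| 1.0 | 28.8/34 = 0.85 | 36.8/42 = 0.88 | 0.80 |
| 1.5 | 32.8/34 = 0.96 | 44.8/42 = 1.07 | 0.80 |
| 2.0 | 36.8/34 = 1.08 | 52.8/42 = 1.26 | 0.80 |

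The benefit is fully cancelled at R = (34 − 20.8)/8 = 1.65 for 8 weeks, or R = (42 − 20.8)/16 = 1.33 for 16 weeks.

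**3. What an added comparison could show**

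Assume 0.5 to 2 falls per person-year. Let m be expected falls per person in the window and k the dispersion (0 for Poisson, 1 for negative binomial). With equal rates, the 95% CI for the rate ratio extends either way by a factor exp(1.96 × √[2(1/m + k)/26]). Power to detect a doubling is Φ(ln 2/√[(1/m + 1/(2m) + 2k)/26] − 1.96).

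| Weeks | Rate | Falls per arm | CI factor, k = 0 / 1 | Power, k = 0 / 1 |
|---|---|---|---|---|
| 8 | 0.5 | 2 | 7.1 / 7.6 | 12% / 12% |
| 8 | 2 | 8 | 2.7 / 3.1 | 36% / 27% |
| 16 | 0.5 | 4 | 4.0 / 4.4 | 20% / 18% |
| 16 | 2 | 16 | 2.0 / 2.4 | 62% / 39% |

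Across these assumptions there are 2 to 16 falls per arm, a CI factor of 2.0 to 7.6, and power of 12% to 62%. That supports a descriptive summary, not a test.

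**The case against.** The strongest reply is that falls during training belong to the adverse-event stream and only later falls are an efficacy outcome. Section IV.C lists falls among adverse events, IV.D counts adverse events including falls among what will be documented, and the Aim 2 text names adverse events and future falls as separate items. On that reading, in-training falls would be compared descriptively along with the PRO-CTCAE.

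Part of this stands. Falls during training are plainly a documented measure, so the gap lies in the analysis and not in collection. But documenting is not comparing. The sentence on comparing groups has the PRO-CTCAE as its subject, and IV.C lists that instrument separately from falls. Coverage of diary falls is at best ambiguous, and IV.F contains no adverse-event analysis.

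A second reply is that the outcome is consistently labelled as post-completion, so reporting it under that label makes no claim about training. That is fair, and it is why the point concerns an omitted safety summary and not a biased estimate.

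A third is low yield and uneven ascertainment. The imprecision is real. Staff recording is tied to Tango lessons, and that contact could also prompt diary entries, so relying on the diary and weekly check-ins reduces the imbalance but may not remove it.

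**Conclusion.** The point holds as a gap in the planned analysis: diary falls are collected from both arms during training, and no between-arm comparison of them is planned. Between 24% and 38% of diary weeks fall outside the randomised falls comparison. The range comes from the unresolved training length and from counting 6 months as 26 weeks.

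A reader might infer more, and the documents do not support it:

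- *That these falls will never be compared.* The plan is silent, and nothing in it prevents a tabulation.
- *That the missing falls are those that happen while dancing.* The diary covers falls at any time of day throughout the training period.
- *That Tango raises falls, or that the planned result would hide a reversal.* No fall rate or rate ratio is given. In the illustration, an in-training ratio of 1.5 gives a whole-period ratio of 0.96 with 8 weeks of training and exceeds 1 only with 16. Both inputs are assumed.
- *That statements about falls after training should be made conditional on the in-training result.* Showing both periods side by side is enough to close the gap.

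This is a worthwhile, inexpensive improvement to safety reporting. It does not affect the primary analysis or the sample size.

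**What to change.** In section IV.F, add a descriptive safety summary of falls for the training period, by randomised arm and limited to the randomised survivors. Show the number of falls, the number of participants with at least one fall, person-weeks observed, and a rate ratio with 95% CI. State that it is not a powered test.

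Base it on the daily diary and weekly check-ins, which both arms complete. Do not add the staff recording made before Tango lessons, since that could inflate the Tango count. Define one window for both arms, from the start of the intervention to its scheduled end, and present the summary beside the 6-month post-intervention result.

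The statements on training length (16 sessions, twice-weekly lessons, week 16) must be reconciled so that this window, and the start of the post-intervention one, are defined.

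The cost is one paragraph and one table, with no new data, visits or participants. The downside is an imprecise estimate that may make the overall falls result look less favourable.

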Prospective 1:1 block randomized study, with random block sizes. Two arms: experimental and active control (Fig 1).

B. Sample

Individuals with breast cancer-related neuropathy will be recruited for this study using the following inclusion and exclusion criteria.

Inclusion criteria:

- Breast cancer survivors \geq 40 years old
- Symptomatic for neuropathy (CIPN20 sensorimotor score < 95 on transformed scale (100 maximum));
- postural control outside 70% CI for adults who are middle-aged without neurotrauma [20]);
- having completed taxane-based chemotherapy treatment at least 3 months ago;
- able to understand and comply with directions associated with testing and study treatments.

Exclusion criteria:

- Pre-existing vestibular deficit;

[figure not shown]

Fig1: Study design flowchart. TP = Testing timepoint.

- poorly controlled diabetes (hgA1C \geq 8);
- non-ambulatory or lower extremity amputation (assistive devices allowed);
- use of cytotoxic therapy during study (immune- and endocrine therapy allowed);
- participation in physical therapy during the study;
- contraindication to participate in Tango due to orthopedic issue (e.g., herniated vertebral disc);

In addition, survivors who are screened and found eligible to participate in this RCT will be asked to invite a companion to enroll with them in the study arm that the survivor is randomized into. (n=up to 100 companions)

Finally, up to 100 survivors screened who do not meet the criteria above will be offered enrollment without compensation in the intervention of their choice, along with their companion (up to n=100), as we have capacity to include them and using the “companion” consent form. Capacity will be defined based on space and staffing availability.

Therefore, in total, up to 200 survivors and up to 200 companions will be enrolled in Phase 2 of this protocol.

C. Measurement/Instrumentation

Data collected at baseline x 4, mid-intervention and post intervention (*collected at baseline x1 only):

- Adverse events (i.e., PRO-CTCAE[26], falls or loss of balance, illness or hospitalization since last visit)
- SF-36[25]
- EORTC QLQ-C30[15]
- Neuropathy symptoms: measured using original or modified forms of the EORTC CIPN-20[16]
- Sports Concussion Assessment Test (SCAT) Symptom inventory (for comparison to CIPN-20)[27,28]
- Pain: measured using original or modified forms of the Brief Pain Inventory (BPI)[29]

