
Data collection: data may be collected using paper or electronic (e.g. MyCAP) versions of approved instruments.

Data storage: paper versions of source documentation will be kept in a locked cabinet within an OSU office that is accessible only to OSU clinical or research staff. Electronic data may be stored in a password protected spreadsheet or through RedCAP.

Interventions: training may be delivered in-person, via video conferencing, or via asynchronous instruction.

E. Internal Validity

All measures will be conducted by a researcher trained in the administration of the measure.

F. Data Analysis

Sample Size Justification: Preliminary data from our group was used to determine sample size requirements for this proposed randomized trial. **Aim 1:** Five cancer survivors with postural control deficits (RMSml>4.0mm) at baseline who participated in Tango practice improved RMSml from mean(SD) of 7.9(1.2) at baseline to 4.6(0.5) after 8 Tango sessions. Assuming more heterogeneity in our analysis sample, (SD=2.7 in control and intervention groups) we estimate Cohen's $d=1.22$. Thus we require an analysis sample of $n=14$ participants per group to provide 85% power at a 5% type I error rate. To account for anticipated drop-out and Aim2 analysis we will **enroll n=26 participants per group.** **Aim 2:** Preliminary data shows an Coefficient of Variation gait speed (CVspeed) SD of approximately 1.2 among survivors with neuropathy and postural deficits prior to Tango practice. With a sample size of $n=19$ per group (per Aim1) and this SD, we have 80% power to detect a difference of 1.32 ($d=1.1$). A cohort of 7 survivors with heterogeneous treatment progress (during and after chemotherapy exposure), not screened for or limited to those with postural control deficits, demonstrated a decrease in CVspeed ($p=0.003$) from 3.0(1.15) to 2.2(1.10) after ≤ 16 sessions of Tango practice ($d=0.711$). We will enroll **n=26 participants per group** to detect a reduction of this magnitude with 80% power.

Statistical Analysis Plan: Unless otherwise noted, all analyses will be performed on an intent-to-treat basis, and all hypothesis tests will be two-sided and at the 5% significance level. Enrolled participant characteristics will be summarized by assigned treatment groups.

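### The planned Pearson correlations have no arm term, time point or scale; pooled over arms on post-treatment or change values, they would mix the treatment contrast into the individual-level association

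*Combined protocol and SAP*

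**What the plan says.** All of this stands in the combined protocol and SAP, mostly in Section IV.F, Data Analysis (Phase II).

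- Aim 1 correlations: "Pearson's R will be calculated to correlate postural control and balance outcomes, PROs, and future falls incidence".
- Aim 2 correlations: "the correlation between biomechanical mobility outcomes, PROs, and falls incidence following intervention completion (Pearson's R").
- Treatment is modelled in the linear mixed model: "Fixed effects will be included for time, treatment, treatment-by-time interactions, and concurrent medication use". Further adjustment is tied to chance imbalance in the group comparison: "we will adjust for potential confounders including baseline RMSml, age, body mass index, concurrent medications". Neither provision is extended to the correlations.
- The default test is stated generally: "all hypothesis tests will be two-sided and at the 5% significance level". The exception for Aim 2, "linear mixed models; one-sided hypothesis test", is attached to the group comparison.
- Section IV.A gives the design: "Prospective 1:1 block randomized study, with random block sizes".

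The plan does not say whether the correlations are computed over both arms, within each arm, or given arm. It also does not say whether posture, gait and PRO values are taken at baseline, after treatment, or as changes. Falls are the exception on timing: Sections IV.C and IV.D have them collected for six months after the intervention, so the falls variable is necessarily post-randomisation.

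**The concern.** Pearson's R is a two-variable statistic. With no arm term named, the plain reading is one coefficient per pair over all participants. In a two-arm trial that coefficient combines two things: how the outcomes go together among people in the same arm, and the single contrast between the arms. If treatment moves both outcomes, the scatter is two displaced clouds, and R departs from zero whether or not the outcomes are related within a cloud.

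The trial is designed in the expectation of such displacement. Section IV.D hypothesises greater improvement under Tango in sway and in gait variability, and Section IV.F plans similar between-arm analyses for PROs and falls. The distortion therefore grows with the success of the intervention. At stake is whether a reported coefficient can support a statement such as: people who sway less have fewer symptoms or falls. A pooled R cannot separate that from: the arms differ on both.

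**Working it through.** **Inputs.** From Section IV.F: pilot RMSml means 7.9 and 4.6 mm, planning SD 2.7, d=1.22; CVspeed d=0.711; 14 per group (Aim 1 requirement), 19 per group (used in the Aim 2 calculation), 26 per group (enrolment). Allocation is 1:1, so p=0.5. No effect is given for TUG, PROs or falls; their values below are assumed.

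**The plan's own figure.** d = (7.9 − 4.6)/2.7 = 3.3/2.7 = 1.22. A two-sided 5% t-test with 85% power needs 13.1, so 14 per group, as stated (power at 14 is 87.4%). The planned effect is reproduced. The plan gives no figure for the correlations.

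**Pooled correlation.** Let ρ be the within-arm correlation, and d1 and d2 the arm differences in within-arm SD units. Then

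R = [ρ + p(1−p)·d1·d2] / √{[1 + p(1−p)·d1²]·[1 + p(1−p)·d2²]}.

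With ρ=0, p(1−p)=0.25 and d1=1.22, the first bracket under the root is 1 + 0.25×1.488 = 1.372.

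- d2=0: numerator 0, so R=0.
- d2=0.3: 0.0915/√(1.372×1.0225) = 0.08.
- d2=0.5: 0.1525/√(1.372×1.0625) = 0.13.
- d2=0.711: 0.2169/√(1.372×1.126) = 0.17.

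**Rejection rates.** These come from 40,000 simulated trials per scenario, with normal outcomes, no within-arm correlation, and a two-sided 5% test of the pooled R.

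| d1 | assumed d2 | pooled R | 14 per arm | 19 per arm | 26 per arm |
|---|---|---|---|---|---|
| 1.22 | 0 | 0 | 5.0% | 5.0% | 5.0% |
| 1.22 | 0.3 | 0.08 | 6.8% | 7.7% | 8.5% |
| 1.22 | 0.5 | 0.13 | 9.9% | 12.0% | 14.7% |
| 1.22 | 0.711 | 0.17 | 14.4% | 18.4% | 24.2% |
| 0.711 | 0.3 | 0.05 | 5.9% | 5.9% | 6.4% |
| 0.711 | 0.5 | 0.08 | 6.9% | 7.6% | 9.0% |
| 0.711 | 0.711 | 0.11 | 8.8% | 10.2% | 12.5% |
| 0.3 | 0.3 | 0.02 | 5.2% | 5.3% | 5.4% |

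Rows with d1=1.22 stand for RMSml paired with a PRO or falls (Aim 1). Rows with d1=0.711 stand for CVspeed paired with a PRO or falls (Aim 2). In the same simulations the partial correlation given arm averaged 0.00 and rejected between 4.7% and 5.3% of the time in every scenario run.

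**The distortion is not only upward.** With d1=1.22 and d2=0.711, a within-arm ρ of −0.2 gives (−0.2 + 0.2169)/1.243 = 0.01, so a real association is hidden. A ρ of 0.3 becomes (0.3 + 0.2169)/1.243 = 0.42.

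**The case against.** **Pooling and timing are inferred from silence.** A reader might infer that the plan commits to a pooled R on on-study values. It does not say so. Section IV.D supports RMSml partly by its value for predicting falls, so baseline sway against later falls is a possible reading. Baseline values in a randomised trial do not differ systematically by arm and would not carry the artefact. The Aim 2 sentence can even be read as comparing correlations between groups. This stands, and it is why the point is conditional. It does not remove the point, because the text as written permits the distorted analysis and nothing in it excludes that.

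**Larger sizes are not supported.** If both outcomes differed by 1.22, pooled R would be 0.27 and about 52% of trials would reject at 26 per arm. A reader might take that as the expected size. The documents plan 1.22 for RMSml alone, so it is not. Posture with gait is not explicitly listed as a pair, so 1.22 with 0.711 is also illustrative. Both planned effects come from uncontrolled pre-post pilots of 5 and 7 people, and effects against an active control may be smaller. Enrolment of 26 per arm includes room for drop-out, so the 14 and 19 per arm columns also matter.

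**No hypothesis about R is stated.** The plan says the coefficient will be calculated, and a non-zero pooled R is a true marginal association. This stands too: the rejection rates matter only if R is tested or read as a within-person-group association.

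**Mechanistic use is not tied to these coefficients.** Section IV.D calls gait variability a behavioural mechanism worth studying, but in hedged terms, and leaves work on recovery mechanisms to later trials. It cannot be said that the trial will misreport the correlations, only that the planned statistic would not protect against it.

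**Conclusion.** The point holds in conditional form. The correlation sentences for both aims leave out arm, time point and scale. If they are carried out on post-treatment or change values over both arms, and Tango moves both members of a pair, R reflects the treatment contrast as well as any association within arms.

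With no within-arm association and d=1.22 on one outcome, the pooled R runs from 0 to 0.17 as the assumed second effect runs from 0 to 0.711. Rejection at 26 per arm runs from about 5% to 24%; at the top of that range it is about 18% at 19 per arm and 14% at 14 per arm. For Aim 2 pairs starting from 0.711 the inflation is smaller, at most 12.5% over the same range. If only one outcome moves there is no distortion, and if both move by 0.3 it is negligible.

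These sizes rest on normal outcomes and equal within-arm variances. For falls, which are counts, the rejection rates are indicative only. A reader might infer that the trial's main result is affected. It is not: the primary difference-in-difference comes from the mixed model, which includes treatment. Severity is minor to moderate.

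**What to change.** Amend the correlation sentences for both aims in Section IV.F as follows.

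1. Make the partial correlation given randomised arm the main coefficient for each pair (equivalently, test one outcome in a regression on the other with arm as a covariate).
2. Show the coefficient within each arm descriptively, since the partial correlation summarises a common association.
3. State the time point and scale of each variable: baseline, post-treatment or change.

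An unadjusted R may still be shown if it is labelled as the overall association.

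The cost is one degree of freedom per correlation, one or two sentences in the plan and slightly more reporting. No new data are needed. If treatment moves neither outcome or only one of them, almost nothing is lost.
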